14.0 Withdrawal of Subjects*

We do not anticipate any withdrawal of subjects or early termination.

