Study measures. Qualitative data will be collected using questionnaires and a semi-structured interview to collect feedback on the FOREVR VR platform content and usability, preoperative VR-BF education and training, postoperative application of VR-BF, and perceived efficacy. Review of patient daily use obtained from FOREVR VR will provide quantitative data about frequency and duration of VR-BF use. As mentioned below, we will assess sensitivity to change of physiological parameters (HRV, respiratory rate) to different frequencies and durations of VR-BF use (dose).¹¹⁷ This data will assist us in determining an appropriate dose (frequency and duration) of VR-BF for training and postoperative pain management to be trialed in Phase 2. Iterative refinements to the VR-BF treatment protocol will be made throughout Aim 1 based on this data. Refinements will be documented, tracked, and applied by the study team.

[figure not shown]
Aim 2: We will conduct a pilot clinical trial to assess the feasibility and acceptability of the VR-BF protocol defined in Aim 1. Feasibility will be assessed by rates of recruitment, enrollment and randomization, retention, and adherence. Acceptability will be assessed by treatment/study burden, satisfaction, treatment credibility, and intervention tolerability. Qualitative data will also be used to assess feasibility and acceptability.

Patient Groups. Seventy patients with the same inclusion/exclusion criteria described in Aim 1 will be randomized to 1 of 2 groups in a 1:1 ratio: VR-BF or attention control condition using a web-based application (www.randomizer.org). The randomization scheme will be generated prior to the start of the study and patients will be randomized based on subject number. We will use the

Feasibility and Acceptability of Technology-Based Interventions in the Perioperative Setting

protocol generated in Phase 1 to apply either the VR-BF or control condition. Control patients will use the *Manage My Pain* application analogously to VR-BF per the protocol developed in Phase 1. Like the VR-BF group, patients will receive scripted instruction on the benefits of mind-body therapy. We will recruit a total of 70 patients to participate, with 35 in each group. Both patient groups will receive a handout detailing the intervention and what they can expect with participation in the study.

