After surgery, as in Aim 1, a trained CRC will visit patients daily or as needed while hospitalized. Control group patients will complete a daily application-generated usage report (date, time, duration); VR-BF patients will have this information, along with HRV and respiratory rate data, obtained from the device. To help determine what outcomes may be impacted by VR-BF for future trial development, patients will also be asked to document pain and anxiety scores before and after each VR-BF or application session using the NRS.^{110,111} Patients will self-report and document these scores before each session and then immediately, 15 minutes, and 30 minutes after session completion. All pain scores and opioid consumption (in morphine equivalents mg/kg/day) will be collected from EPIC, the electronic medical record, for each 24-hour period during study enrollment; anxiety scores are not documented by the nursing staff so only self-reported scores will be used. Documented pain scores will also help finalize the “dose” of VR-BF to be used in the efficacy trial as we will assess for correlation, if any, between pain score and use of VR-BF. At the final study visit prior to discharge, patients will answer a questionnaire and engage in a semi-structured interview soliciting qualitative feedback about their experience with the intervention or control to finalize the study protocol for the clinical efficacy trial. Participants will be given the option to take the VR-BF platform home or continue using the *Manage My Pain* application for up to two weeks after discharge. If this option is selected, patients will complete a daily log/report documenting use, pain scores, and opioid consumption. During the first postoperative clinic visit, VR-BF and reports/logs will be collected and questions about home use will be asked, answered, and recorded. Parents will also be asked to complete a survey about their experience and opinions. If patients cannot be met during the first postoperative clinic visits, other arrangements will be made to collect the information and equipment.

Feasibility and Acceptability of Technology-Based Interventions in the Perioperative Setting

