Data Collection (Table 3). **Feasibility.** *Recruitment:* The number of patients screened per month will be recorded and assessed for eligibility; reasons for ineligibility will be recorded. If 80% of patients do not meet criteria, we will adjust criteria as necessary. *Enrollment and randomization:* Enrollment and randomization will be defined as agreeing to participate in the study and being willing to be randomized. We will record the number of eligible patients approached and enrolled each month. We will collect reasons for refusal to enroll, including unwillingness to be randomized. If rates are not maintained at 80%, we will adjust strategies accordingly. *Retention:* We will define retention as the number of patients who complete the study by participation in the last study visit for both arms. We will collect reasons for dropout. If $\geq 80\%$ retention is not maintained, we will evaluate reasons for dropout. *Adherence:* We will define adherence to preoperative training as completion of the education and training session with the study team and completion of $\geq 5/7$ daily sessions. Adherence to postoperative VR-BF/app use will be defined as completion of $\geq 5/7$ daily sessions. Our target will be $\geq 80\%$ completion. We will collect reasons for failure.

Questionnaires and the semi-structured interview will also assess feasibility using measures based in the literature.¹¹⁹

Acceptability. Treatment/Study

Burden: Burden will be assessed by collecting data on daily log completion, data from questionnaires, and participation in the interview. We will collect reasons for drop out to better understand treatment and study burden.

	Measures	Definition	Benchmarks	Additional Data
Feasibility	Recruitment	Number of patients screened per month	$\geq 80\%$ will meet eligibility criteria	Reasons for not meeting criteria
	Enrollment and randomization	Number of patients approached who agree to enroll in the study and be randomized to a treatment arm	$\geq 80\%$ of those approached will agree to enroll and be randomized	Reasons for refusal, including unwillingness to be randomized
	Retention	Number of participants who complete the study as defined by participation in the last study visit	$\geq 80\%$ retention	Reasons for dropout
	Adherence	Treatment-specific adherence	$\geq 80\%$ will complete ≥ 1 session per day for $\geq 5/7$ days (preop) and ≥ 1 session per day (postop)	Reasons for failure

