12.0 Local Number of Subjects

Total number of subjects to be accrued locally: up to 102

We anticipate a $\geq 80\%$ recruitment and retention rate

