Qualitative analysis. From the questionnaires and semi-structured interviews, we will compile data on satisfaction, credibility, and tolerability as well as additional feasibility data. This qualitative data will be analyzed in the same way as in Aim 1.

Sample size. Seventy subjects will be enrolled and randomized to one of two study arms: intervention and active control. As this is a pilot feasibility and acceptability study, no confirmatory hypothesis testing will be done. Our sample size is based on estimation of two-sided CIs for one proportion with exact formula of the binomial probabilities. To estimate a 95% CI with targeted width of 0.22 and an assumed proportion of 80%, we will need a sample size of 70 (35 per group), resulting in a total of 56 patients (28 per group) included in the analysis after 80% retention.

Anticipated outcomes. We anticipate creating a final VR-BF study manual that will define study procedures for an efficacy trial and provide key pilot data for future grant applications. By the end of Phase 2, we expect to have 1) A defined patient population with clearly delineated eligibility criteria; 2) A clearly delineated preoperative education and training protocol for VR-BF/active control; 3) A dosing strategy (frequency, duration) for postoperative administration of VR-BF/active control; 4) Feasibility and acceptability data for VR-BF/active control; and 5) A preliminary assessment of key outcome measures (pain, anxiety, opioid consumption) to be evaluated in the efficacy trial.

Data Safety:

Data confidentiality will be maintained by data being stored in a password protected computer and any hard copies of patient information stored in a locked office. Data will be transmitted to a password-protected Nationwide Children's computer for further analysis. Data held in REDCap is deemed secure. All individuals using and interacting with this data will be trained appropriately and a member of the study team. Any data transmission will occur via secure emails (not personal). Proper agreements have been executed to cover the sharing of de-identified data from REDCap with a statistician at CCHMC. Data will be de-identified by selecting the option to export data directly from REDCap with all known identifier fields (date, name, address, MRN, etc.) removed. The exported data set will then be shared with CCHMC. Data will be stored for the duration of the study and analysis/presentation up to the time period specified by the IRB.

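### Section 14 expects no withdrawals although the sample size allows for losing 14 of 70, and patient-rated satisfaction and credibility are scheduled with no provision for patients who stop early

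*Combined protocol and SAP*

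**What the plan says.** **On withdrawal.** The whole of Section 14.0 is one sentence: "We do not anticipate any withdrawal of subjects or early termination". It gives no procedure for a patient who leaves.

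**On expected loss.** Other sections assume that some patients will be lost:
- Section 17.0, Aim 2 Sample size, arrives at 70 randomised, "resulting in a total of 56 patients (28 per group) included in the analysis after 80% retention".
- Section 12.0 anticipates at least 80% for the "recruitment and retention rate".
- Section 6.0, Data Collection, defines retention by attendance at the last visit and adds "We will collect reasons for dropout".
- Section 15.0, Clinical Care, lets patients end participation whenever they wish.

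**On the ratings.** Section 6.0 bases satisfaction on the questionnaire and interview, and treatment credibility on the survey and interview. For Aim 2 the timing is: "At the final study visit prior to discharge, patients will answer a questionnaire and engage in a semi-structured interview". The self-reported measures paragraph in the same section places the patient survey at the end of participation and does not say what happens if participation ends early. The parent survey is described together with the first postoperative clinic visit.

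**On analysis.** Section 17.0 promises rates, variances and 95% confidence intervals for quantitative satisfaction and credibility data. It gives no denominator and no rule for patients without a rating. Table 3 sets no benchmark for either measure.

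**The concern.** Two things do not fit together. First, a plan that expects no withdrawals has no reason to say what is collected from a patient who withdraws, yet the sample size is built on one in five being lost. Second, the visit at which patients rate the intervention comes at the end of the hospital stay. A patient who gives up during the preoperative practice week supplies a reason for dropping out, but no satisfaction or credibility rating.

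Section 2.0 treats acceptability of both arms as essential for the later efficacy trial. Patients who stop because they dislike an arm are among the most informative raters of it. If they are missing, the two rating-based measures describe a selected group. If the arms lose different numbers of patients, or lose them for different reasons, the two sets of ratings also rest on differently selected patients.

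**Working it through.** **Inputs.** From Section 6.0: "We will recruit a total of 70 patients to participate, with 35 in each group". From Section 17.0: "To estimate a 95% CI with targeted width of 0.22 and an assumed proportion of 80%, we will need a sample size of 70"; the interval method, "two-sided CIs for one proportion with exact formula of the binomial probabilities"; and 56 analysed after 80% retention. The satisfaction counts below are assumptions for illustration, because the documents give none and set no threshold for calling a patient satisfied.

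**Step 1: reproduce the plan's figure.** Width of the exact (Clopper-Pearson) 95% interval at a proportion of 0.80:

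| n | Width |
|---|---|
| 56 | 0.222 (45/56) to 0.223 (0.8 × 56 = 44.8) |
| 70 | 0.199 |

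The target of 0.22 corresponds, after rounding, to the 56 retained patients and not to the 70 randomised. (A width of strictly 0.220 or less would need 58.) Inflating for loss gives 56 / (1 − 0.20) = 70. The stated 70 is therefore reached only by allowing for 20% loss.

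**Step 2: size of the planned loss.** 70 − 56 = 14, or 35 − 28 = 7 per arm, which is 20% of those randomised.

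**Step 3: effect on one arm, if all seven are unrated.** Suppose 25 of the 28 retained patients are satisfied.
- Among those rated: 25/28 = 89.3%, exact 95% CI 71.8% to 97.7%.
- Worst case, none of the seven satisfied: 25/35 = 71.4%.
- Best case, all seven satisfied: (25 + 7)/35 = 32/35 = 91.4%.
- If two of the seven were satisfied: 27/35 = 77.1%.

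For the whole randomised arm to match 89.3%, 0.893 × 35 − 25 = 6.25 of the seven would have to be satisfied. Six of seven gives 31/35 = 88.6%, slightly below the rate among those rated. Only seven of seven puts the arm above it.

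**Step 4: both arms together, for other completer rates.**

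| Satisfied among 56 rated | Rate | Range over all 70 |
|---|---|---|
| 45 | 80.4% | 45/70 = 64.3% to 59/70 = 84.3% |
| 50 | 89.3% (exact 95% CI 78.1% to 96.0%) | 50/70 = 71.4% to 64/70 = 91.4% |
| 54 | 96.4% | 54/70 = 77.1% to 68/70 = 97.1% |

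The range is always 14/70 = 20 percentage points wide, whatever the completers say. The confidence interval among raters does not include this uncertainty.

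**Step 5: why seven is an upper figure at the planned retention.** Retention means attending the last visit, and the documents do not say whether that is the pre-discharge visit or the postoperative clinic visit. If it is the clinic visit, some patients counted as lost will already have given ratings before discharge.

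**The case against.** The strongest reply is that this is a descriptive pilot with no benchmark on satisfaction or credibility, so no stated decision rule changes. Section 14.0 is then a single sentence to align. Non-retention (a missed last visit) is broader than withdrawal, and the 20% is a planning allowance. A survey at the end of participation could, on its plain words, cover participation that ends early. The CONSORT diagram and the completion percentages should already show most of the numbers randomised and rated.

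Much of this stands. It makes the point modest, and it rules out several stronger readings that a reader might infer:

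- **That acceptability as a whole is rated by completers alone.** Burden is the percentage completing the study measures, so a missing questionnaire counts against the arm. Tolerability is the percentage of patients with adverse events. Neither is limited to completers, and reasons for dropout are collected.
- **That every rating is taken before discharge.** The parent survey and the home-use questions are described with the postoperative clinic visit, with other arrangements if patients cannot be met there. This does not supply the patient's own credibility rating, and the arrangements address a missed clinic visit, not early stopping.
- **That pain and opioid data from the medical record would cease when a patient stops using the device.** The Additional Data Collection text in Section 6.0 sets that window as the hospitalisation.
- **That the plan does not separate stopping the device from leaving the study.** Section 6.0 defines adherence and retention separately, each with its own reasons for failure.
- **That the ratings are certain to be inflated.** The best case (91%) lies above the completer rate (89%).

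What the reply does not remove is that the operative Aim 2 text fixes the patient questionnaire at the pre-discharge visit, and no section says that an early stopper receives it. A reason for dropping out is not a rating and cannot enter the promised rates and intervals.

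**Conclusion.** The point holds in a limited form. Section 14.0 contradicts the 20% loss on which the Aim 2 sample size depends. Patient-rated satisfaction and treatment credibility, two of the four acceptability measures, will come essentially from retained patients. Their figures are likely, but not certain, to be more favourable than for all randomised.

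At the planned retention up to 7 of 35 per arm are unrated, leaving 20 percentage points undetermined (71% to 91% in the example). This rests on three assumptions: loss occurs at the planned 20% and equally in both arms; every lost patient is unrated; and the satisfaction counts are illustrative. The expected direction rests on the further, plausible but unshown, premise that patients who stop are less satisfied. No stated benchmark is affected, so this is an inexpensive improvement and not a flaw that threatens the trial.

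**What to change.** 1. In Section 14.0, replace the sentence with the 80% retention assumption of Section 17.0, and say what is collected from a patient who withdraws.
2. In Section 6.0, state that any patient who stops or withdraws early is offered the same satisfaction and credibility questionnaire at that time, by REDCap or phone. State also which visit counts as the last one for retention.
3. In Section 17.0, report satisfaction and credibility by arm with the number randomised and the number rated, show early stoppers separately from completers, and give best- and worst-case bounds for those with no rating.

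The cost is protocol wording and earlier use of an existing form for about 14 patients. The downside is that the figures may be less favourable, and some withdrawing patients will decline the form. The bounds in item 3 keep the result interpretable when they do.

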15.0 Risks to Subjects*

There are minimal physical risks to participants and enrollment in this study will not alter their management. All patients will receive pain management per the Acute Pain Service during the duration of the study.

Clinical Care. Enrolled patients will receive the same care and attention in the postoperative period or during their hospital stay as those non-enrolled patients. Patients will be given the opportunity to end participation in the study at any time.

VR Headset. VR headsets used in this study are minimal risk devices, and because they are considered a relaxation device by the FDA, they are not regulated. Risks specific to this research study are minimal or absent with the greatest risk being motion sickness while the headset is in place¹¹³ and a theoretical risk of inducing seizures (0.025% in pediatric data supplied by a similar Samsung device). Should motion sickness occur, the participant will be instructed to remove the device to ensure resolution of symptoms; we will exclude patients with a history of seizure disorder or other relevant neurological conditions. Other adverse events will be defined using standard criteria. The researchers shall monitor the patient while the device is applied. Serious adverse events, although unanticipated, will be reported using routine avenues. The Starlight Xperience device was used in our pilot study (**CCHMC IRB #2018-2892**) without any documentation of adverse effects. We have since purchased new headsets, the Oculus Quest and Oculus Quest 2, which have been used in prior studies without any reported adverse events (**CCHMC IRBs #2019-1090, 2020-0258, 2020-0612**). We will continue updating to newer versions of the Oculus/Meta Quest as they become available when new equipment is required.

FOREVR VR. This device has been approved for both research and clinical use by the Equipment and Standards Committee at Cincinnati Children's Hospital. It is a noninvasive device to measure respiratory rate (via chest movement) and heart rate using an ear clip. This device is also considered a minimal risk device. This is the first study to use FOREVR VR.

HeartMath Inner Balance. If FOREVR VR is unable to be used, we will use HeartMath Inner Balance as a back-up means to collect heart rate and use data (www.heartmath.com), a commercially available biofeedback device. HeartMath Inner Balance is also considered a non-invasive device and uses an ear clip (analogous to FOREVR VR) to collect heart rate data. There is minimal risk with the use of this device.

We do not anticipate any psychological, social, legal, or economic risks to this study. We also do not anticipate risk to others who are not subjects in this study.

